10.5 Duration of Response (DOR)

DOR will be calculated for patients who achieve CR or PR regardless of confirmation. For such patients, DOR is defined as the number of months from the start date of PR or CR (whichever response is recorded first), to the first date that progressive disease (PD) or death is documented.

The same censoring rules of the primary PFS analysis will be applied to DOR.

Median DOR will be estimated according to the Kaplan-Meier method. Inferential comparison between treatment arms for DOR is not planned.

As noted previously, the primary analysis of DOR will be based on the time point and best overall responses and PFS events determined by blinded independent central review. A supplemental analysis of DOR will be performed based on investigator assessments using the same data cutoff and censoring rules specified in PFS for the primary analysis.

10.6 Overall Survival (OS)

OS is defined as the time from randomization to the date of death due to any cause. Patients who are alive or lost to follow-up as of the data analysis cutoff date will be censored at last known alive date before cutoff.

The OS will be summarized descriptively using the Kaplan-Meier method. Median follow-up for OS will be estimated according to the Kaplan-Meier estimate of potential follow-up ([Schemper 1996](#)). The KM plot will be produced by treatment arm.

The primary inferential comparison of this endpoint will use the stratified log-rank statistic to test the null hypothesis that the distribution of OS times is equal for the 2 treatment arms.

Subgroup analyses will be performed for the subgroup factors listed in [Section 10.2](#). For each subgroup, the hazard ratio for treatment arm will be estimated and the KM plot will be produced. Forest plots will be used to graphically display the hazard ratios and 95% confidence intervals across subgroups. Kaplan-Meier estimates will be provided for each treatment arm within each subgroup.

Survival rate at one-, two-, and three-year after randomization will be estimated for each treatment arm using the Kaplan-Meier product-limit method. Greenwood's formula will be used to calculate the standard error of the Kaplan-Meier estimate and corresponding 95% confidence interval.

To supplement the analysis of OS, a summary of the subsequent anti-cancer therapies and interventions initiated after the discontinuation of study treatment will be provided. Such therapies will be collected during the scheduled post-treatment follow-up assessments.

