4. Disease assessments will be performed every six weeks (+/- 1 week) for six months (i.e., weeks 6, 12, 18, 24), every 9 weeks (+/- 2 weeks) thereafter (i.e., weeks 33, 42, 51, 60, 69, 78, etc.), until progression. Patients who discontinue study treatment without documented progression of disease as per RECIST 1.1 should continue to have Disease Assessment Visits until such criteria are met (regardless of intervening therapy). In the event that follow-up is discontinued without a final disease assessment documenting objective disease progression, the reason must be supplied; in particular, any admittance to hospice or other such similar end-of-life care must be reported. If a partial or complete response is noted, a follow-up radiographic assessment must be done no sooner than 28 days later to confirm response. If surgical intervention or localized radiation become indicated (either for palliation or down-staging of previously non-resectable tumor), these interventions should be avoided if clinically feasible until after the 12 week response assessment. Prior to any intervention (such as surgical resection, palliative radiation or alternate anti-cancer therapy), every effort should be made to perform a tumor response assessment in order to document progression and/or confirm an objective response. Patients who undergo surgical resection or radiation in the absence of progression may continue to receive study treatment until remaining lesions meet criteria for progression of disease.
5. Subsequent to the End of Treatment Visit, all patients will be followed at 12 (±2) week intervals until study closure. These visits may be performed by telephone. However, for patients who discontinue study treatment in the absence of progression, survival assessments may be combined with Disease Assessment Visits, and conducted every 6 (±1) or 9 (±2) weeks until progression, and then at 12 (±2) week intervals until study closure.
6. The End of Treatment Visit should be performed within 28 days after last dose of study treatment and prior to initiation of alternate therapies.
7. Assessments do not need to be repeated if completed within the previous 24 hours as part of the screening assessment.

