10.1.5. Survival Follow-up

Subsequent to progression of disease, all patients will be followed at 12 week intervals until study closure.

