OS is defined as the number of months from randomization to the date of death due to any cause. Patients who are alive or lost to follow-up as of a data analysis cutoff date will be right-censored. The censoring date will be determined from the patients' date of last contact. OS will be summarized descriptively using the Kaplan-Meier method. Inferential comparisons between treatment arms will use the stratified log-rank test. Stratification will be based on the stratification factors used for the randomization. The hazard ratio for treatment will be estimated using a stratified Cox proportional hazards model.

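### SAP 10.6 counts deaths up to the cutoff but ends survivors' follow-up at the last contact before it, so Kaplan-Meier OS is biased downward to the extent that deaths in that gap become known

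*SAP*

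**What the plan says.** - **Event.** SAP 10.6: "OS is defined as the time from randomization to the date of death due to any cause".
- **Censoring, SAP 10.6.** Patients alive or lost to follow-up at the data cutoff "will be censored at last known alive date before cutoff".
- **Censoring, Protocol 12.5.1.** "The censoring date will be determined from the patients' date of last contact". This is worded differently and is not limited to contacts before the cutoff.
- **Contact schedule.** On treatment, visits are every 3 weeks. After the End of Treatment visit, Table 1 footnote 5 of the protocol says that "all patients will be followed at 12 (±2) week intervals until study closure", and telephone is allowed. For patients who stop treatment without progression, "survival assessments may be combined with Disease Assessment Visits, and conducted every 6 (±1) or 9 (±2) weeks until progression". Protocol 10.1.5: "Subsequent to progression of disease, all patients will be followed at 12 week intervals until study closure".
- **Use of OS.** SAP 10.1 tests OS with ORR by the Hochberg procedure if PFS is positive. SAP 10.6 also plans Kaplan-Meier summaries and one-, two- and three-year survival rates.

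Neither document says how information that arrives between the cutoff and database lock is used. The sensitivity analyses in SAP 10.3.3 concern PFS only. Protocol 7.2.5 (Completion of Study) is not in the text available for this review.

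**The concern.** Take two patients past progression, both last contacted 10 weeks before the cutoff. One dies 5 weeks later and the site reports it before lock: an event on the true date. The other is alive at the cutoff. Read literally, SAP 10.6 censors that patient 10 weeks earlier, even if a call the following week shows survival past the cutoff. Whether the last gap counts as follow-up then depends on the outcome in that gap. Kaplan-Meier estimation assumes that it does not.

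The gap can reach 14 weeks after progression (12 plus the 2-week window). Person-time is removed from survivors while deaths in the same weeks stay in, so curves, medians and landmark rates come out too low in both arms. The planned median follow-up for OS uses the same censoring dates and is shortened too.

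**Working it through.** **The plan's own figures.** HR = 4.0/6.25 = 0.64. Schoenfeld events with 2:1 allocation, two-sided 0.05 and 85% power: (1.960 + 1.036)² / [(2/3)(1/3)(ln 0.64)²] = 8.98 / (0.2222 × 0.1992) = 203. With exponential PFS, uniform 24-month accrual and 10% loss, 204.5 events are expected at 26 months. Both stated figures reproduce, so 26 months is used as the cutoff.

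**Inputs for OS.** From the documents: 24-month uniform accrual, 26-month cutoff, contact every 3 weeks on treatment and every 12 weeks after progression. Assumed: exponential OS with median 8, 10, 12 or 15 months (the documents give none); median PFS 5.5 months for the switch from 3- to 12-week contact; and the share of gap deaths known before lock (100%, 50% or 0%). The 6- or 9-week option for patients off treatment without progression is not modelled.

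**Hand check, median OS 10 months.** The death rate is λ = ln 2/10 = 0.0693 per month.
- Share alive at the cutoff: (e^(−2λ) − e^(−26λ))/(24λ) = (0.8706 − 0.1649)/1.664 = 0.424. About 0.576 × 300 = 173 patients have died.
- Mean follow-up per patient with full information: 0.576/0.0693 = 8.31 months.
- If progression is independent of death, about 34% of the living are unprogressed. With mean lags of half the contact interval, the average lag is 0.34 × 1.5 + 0.66 × 6 = 4.5 weeks, or 1.03 months.
- Follow-up lost per patient: 0.424 × 1.03 = 0.437 month. The crude death rate is inflated by 8.31/(8.31 − 0.437) = 1.056.

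Simulation gives 1.055 for this case.

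**Simulation, 400,000 patients per scenario, 26-month cutoff, all gap deaths known (SAP rule vs truth).**

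| Assumed median OS (months) | KM median (months) | 12-month OS (%) | 24-month OS (%) |
|---|---|---|---|
| 8 | 7.76 vs 8 | 33.9 vs 35.4 | 8.8 vs 12.5 |
| 10 | 9.65 vs 10 | 41.9 vs 43.5 | 14.3 vs 18.9 |
| 12 | 11.51 vs 12 | 48.4 vs 50.0 | 19.9 vs 25.0 |
| 15 | 14.25 vs 15 | 56.0 vs 57.4 | 27.4 vs 33.0 |

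Censoring the living at the cutoff restores the true values (median 10: 43.5%, 28.7% and 18.9% at 12, 18 and 24 months).

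**Share of gap deaths known (median 10, 26 months).** At 50%: median 9.81 months and 24-month OS 16.5%, about half the bias. At 0%: 10.02 months and 19.0%, no bias, because the dead and the living then both leave at the last contact.

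**Cutoff at 36 months, all gap deaths known.** The loss is 0.1 to 0.3 points at 12 months and about 1 to 1.5 points at 24 months. The median moves by 0 to 0.1 month for assumed medians of 8 to 13 months, and from 14.99 to 14.80 at an assumed 15.

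**Comparison of arms.** 4,000 trials of 200 and 100 patients, PFS medians 6.25 and 4.0 months, control median OS 10 months, 26-month cutoff, all gap deaths known, unstratified log-rank (SAP rule vs full follow-up):
- True HR 1: two-sided rejection 5.1% vs 5.0%; mean HR 0.985 vs 0.993.
- True HR 0.8: rejection 29.2% vs 28.1%; mean HR 0.782 vs 0.787.

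The HR shift is 0.985/0.993 = 0.992 and 0.782/0.787 = 0.994, under 1%. The standard error of log HR at 173 deaths is 1/√(173 × 2/9) = 0.16, so the shift is about 0.05 standard errors.

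**The case against.** The strongest reply is that the deciding premise is undocumented. Neither document says that deaths learned after the cutoff are used while evidence of survival learned after it is not. If such information is used for both, or for neither, most of the asymmetry goes. A patient reached after the cutoff is also known to have been alive up to it, so "will be censored at last known alive date before cutoff" could be applied generously, and Protocol 12.5.1 does not restrict the contact to before the cutoff. This stands as a limit on size: the bias scales with the share of gap deaths known. It does not remove the point, because the SAP's literal wording takes survivors back before the cutoff and nothing in it does the same for deaths.

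Four further limits stand.
- A reader might infer that every off-treatment patient is contacted only every 12 weeks. Footnote 5 does not support that: without progression, contact may be every 6 or 9 weeks.
- A reader might infer that no survival check is planned at the cutoff. With Protocol 7.2.5 unavailable, that cannot be established.
- A cutoff 2 months after accrual ends is near the worst case. Only about 300 × 2/24 = 25 patients could then have 24 months of potential follow-up, so the 24-month estimate would be imprecise anyway. Planned three-year rates imply later OS data, where the bias is small.
- With 300 patients, a 0.4-month shift in the median is well inside sampling error (SD about 1.1 months for CDX-011 and 1.6 for capecitabine).

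**Conclusion.** The point holds as a modest, one-directional bias in descriptive OS results, conditional on gap deaths being learned before lock. With assumed OS medians of 8 to 15 months, a 26-month cutoff and all gap deaths known, it is about 0.2 to 0.75 month in the median, about 1.5 points at 12 months and 4 to 6 points at 24 months. It halves if half of those deaths are known and vanishes if none are.

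Because OS is a Hochberg-tested endpoint and more CDX-011 patients would still be on 3-weekly visits, a reader might infer a threat to the test or a material tilt toward CDX-011. The plan's design figures do not support either: in the simulation, rejection under the null and the hazard ratio hardly move. What is at stake is the accuracy of the reported curves, medians and landmark rates. This is a cheap improvement to a stated rule, not a flaw in the inference.

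**What to change.** **SAP 10.6.** Censor at the cutoff date any patient shown to have been alive then by a contact on or after the cutoff, including a patient whose death is dated after it. Use the last known alive date only for patients with no such contact and no death known on or before the cutoff. State that information received between cutoff and lock is used in the same way for deaths and survivors, and align Protocol 12.5.1 with this wording.

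**Survival status.** If no sweep is already planned, telephone patients not known to have died at about the cutoff, as footnote 5 already allows. If a sweep is not feasible, add a sensitivity analysis that counts deaths only up to the last scheduled contact. In the simulation this also removes the bias (43.5%, 28.8% and 19.0% at 12, 18 and 24 months for median OS 10).

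**Cost.** A short SAP edit and one round of calls: with median OS 10 months, about 0.424 × 300 = 127 patients alive at a 26-month cutoff, spread over 100 to 175 centres. Changing Table 1 or other protocol text would need an amendment with ethics approval under Protocol 14.4; the SAP edit alone would not change the visit schedule.

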10.7 Health-Related Quality of Life (HRQOL)

HRQOL will be assessed in a subset of patients using the EORTC quality of life core questionnaire-30 (QLQ-C30, version 3). The EORTC QLQ-C30 consists of 30 individual items, each representing single- or multi-item scales. Of the 30 questions, 24 aggregate into 9 multi-item scales representing the following HRQOL dimensions: 5 functioning scales (physical, role, emotional, cognitive, and social), 3 symptoms scales (fatigue, nausea and vomiting, and pain), and 1 global measure of health status ([Table 4](#)). The remaining 6 single-item scales assess the following symptoms: dyspnea, insomnia, appetite loss, constipation, diarrhea, and the perceived financial impact of the disease treatment.

The individual items on both EORTC questionnaires will be scaled and scored according to the EORTC QLQ-C30 Scoring Manual ([Fayers 2001](#)). The raw scores will be transformed to a linear scale ranging from 0 to 100, where higher scale scores indicate better HRQOL for the global health status and functioning scales, and worse HRQOL for the symptom scales. Differences from baseline of at least 10 points will be classified as the minimum clinically meaningful change in an HRQOL measure ([Osoba 1998](#); [Maringwa 2011](#)). Changes of more than 20 points will be classified as large effects. For example, an increase of 10 points on a functional scale will represent a moderate improvement, whereas a decrease of 10 points will represent moderate worsening. Changes of less than 10 points will be regarded as no change, or as clinically irrelevant.

The functional scales will be scored as follows:

$$Score = \left\{ 1 - \frac{(RS - 1)}{range} \right\} \times 100$$

where *range* is the difference between the possible maximum and minimum response to individual items. Where the majority of items take values from 1 to 4, giving *range* = 3.

Raw score (RS) is the mean of the component items:

$$RS = (I_1 + I_2 + I_3 + \dots + I_n) / n$$

Similarly, the symptom scales/items and global health status will be scored as follows:

$$Score = \{(RS - 1) / range\} \times 100$$

For multi-item scales, if at least half the items in the scale are complete, then the scale score will be calculated based on the items for which data are available. Otherwise, the scale score will be set to missing. Under this approach, none of the single-item measures will be imputed.

Table 4: Scoring the EORTC QLQ-C30 (version 3.0)

Scales/Items	Number of Items	Item Range	Item Numbers
Global health status			
Global health status	2	6	29, 30
Functional scales			
Physical functioning	5	3	1 to 5
Role functioning	2	3	6, 7
Emotional functioning	4	3	21 to 24
Cognitive functioning	2	3	20, 25
Social functioning	2	3	26, 27
Symptom scales/items			
Fatigue	3	3	10, 12, 18
Nausea and vomiting	2	3	14, 15
Pain	2	3	9, 19
Dyspnea	1	3	8
Insomnia	1	3	11
Appetite loss	1	3	13
Constipation	1	3	16
Diarrhea	1	3	17
Financial difficulties	1	3	28

Baseline HRQOL assessments will be administered to patients prior to randomization. Post-baseline HRQOL assessments are planned for Day 1 of Cycles 3, 5, 7, etc. (i.e., “odd cycles”) and End of Treatment (EOT) visit.

Summarization of the HRQOL data will be based on the actual study visits (including unscheduled visits and EOT visits) mapped at Weeks 6, 12, 18, etc.

If multiple HRQOL assessments are associated with the same time point, the assessment performed closest to the planned study day will be used for purposes of summarizing the data. If 2 measurements are equidistant from the planned study day, the measurement occurring prior to the planned study day will be used for summarization.

The primary HRQOL analysis will be based on the subset of patients in the ITT population who complete the HRQOL questionnaire at baseline.

Missing assessments present a challenge in analyzing and interpreting HRQOL data, especially when the data are missing non-randomly. For example, patients who experience increased toxicity or disease progression, hospice entry, or death are more likely to miss one or more assessments. Similarly, in a longitudinal study data may be missing at later assessments because of death or withdrawal due to disease progression. This leaves purportedly healthier patients, with better HRQOL scores on study longer and displaying a misleading trajectory of higher scores over time. If the reasons for missing data are ignored and the analyses are based only on the observed data, the estimates may be biased in that they do not accurately reflect the entire population of study patients ([Troxe1 1998](#))

Mixed effects models for repeated measures data based on maximum likelihood theory provide valid results when data are missing at random (MAR). Data are MAR if they depend on the observed data only. If the probability of missing depends on the unobserved HRQOL scores, then the missing data are considered non-ignorable, or missing not at random (MNAR). This type of missing data can occur in association with death, disease progression, or toxicity. Distinguishing between MAR and MNAR is not trivial and relies on assumptions that are themselves untestable because the required data are missing. Applications of mixed models have been developed that can assist in the analysis of non-ignorable missing data. One such application is the pattern-mixture models. In this method, patients are stratified by the missing data pattern, and mixed models are created within each stratum. Parameter estimates for each stratum are then combined into a weighted average for the entire study population.

The pattern of missing HRQOL data in this study will be examined with patients classified into groups based on the timing of study dropout for purposes of future HRQOL assessment. The chi-square test and two-sample t-test, as appropriate, will be used to compare baseline characteristics between dropout groups. Because it is not possible to definitively determine whether missing data are ignorable, sensitivity analyses

(comparing the mixed effects model and pattern-mixture model, described below) will be performed to ensure that treatment group effects are consistent across different analytical methods with different missing data assumptions and to evaluate the range of possible treatment group differences.

The initial HRQOL analysis will evaluate the EORTC QLQ-C30 scores (global health status and each individual function/symptom scale) longitudinally using a linear mixed effects model for repeated measures. This model, which assumes missing data are MAR, will describe the rate of change in HRQOL scores over time for each treatment arm, taking into account the between-patient variability by incorporating each patient's individual starting point and individual rate of change. The MIXED procedure in SAS will be used with patients as the random effect; treatment arm will be defined as the fixed effect. The model also will include linear time effects (i.e., week) and time by treatment interaction terms. A covariance structure that follows an autoregressive (AR) process dependent only on the prior HRQOL assessment will be used (i.e., AR-1). If there is model convergence issue, then compound symmetry covariance structure will be used.

Because missing HRQOL data are anticipated to be related to worsening prognosis, a sensitivity analysis will be performed using a pattern-mixture model to assist in the analysis of potentially non-ignorable missing data. For this analysis, patients will be stratified into groups based on their treatment arm and timing of study dropout for HRQOL assessment (anticipated to be largely due to disease progression and death). Patients will be classified as “dropouts” if their last HRQOL assessment was prior to 6 months and as “completers” if their last assessment was 6 months or later. Mixed effects models will be created within each stratum, which will provide for separate estimates of treatment effect for “dropouts” and “completers”. Parameter estimates for each stratum will then be combined into a weighted average for the entire treatment arm. As noted previously, selected demographics and disease characteristics also will be summarized for “dropouts” and “completers” separately to evaluate if the missing HRQOL data are MAR.

A check of the distributional assumptions for the longitudinal models will be performed, along with diagnostics to examine residuals and the presence of any outlying and influential observations. The results from the data checking and model diagnostics will be presented in a separate report.

The HRQOL objective is considered exploratory. For all HRQOL scales, the p-values will be evaluated in an exploratory manner using a nominal significance level of 0.05 (2-sided).

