
Study Treatment Dosing and Administration
	
CDX-011 will be administered on Day 1 of repeated 21 day cycles. The starting CDX-011 dose is 1.88 mg/kg, given as a 90-minute intravenous infusion using a 0.22 µm in-line filter. Treatment will continue until progression or intolerance.
 
Capecitabine will be orally administered on Days 1-14 of repeated 21 day cycles. The recommended capecitabine starting dose is 1250 mg/m² twice daily (equivalent to 2500 mg/m² total daily dose) per the package insert, and subsequent treatment will be dictated by tolerance and institutional practice.

Eligibility Criteria
	
Inclusion Criteria
 
Patients may be included in the study only if they meet all of the following inclusion criteria at the time of randomization:
 
 1. Female or male subjects with metastatic, histologically or cytologically confirmed carcinoma of the breast. 2. Documented progression of disease, based on radiographic, clinical or pathologic assessment showing increased tumor burden or new site(s) of disease during or subsequent to the last anticancer regimen received. 3. Overexpression of GPNMB ($\geq 25\%$ of malignant epithelial cells expressing GPNMB, as determined by a central laboratory using IHC methods) in at least one tumor sample obtained in the advanced setting. 4. Triple-negative status determined in a tumor sample obtained in the advanced setting, according to the following criteria: 
 a. Minimal or no expression of estrogen and progesterone receptors ($<10\%$ of cells positive by immunohistochemistry (IHC)). Patients with low hormone receptor expression (ER and/or PR 1-9%) must be deemed appropriate candidates for cytotoxic chemotherapy by the investigator. b. Minimal or no expression of HER2 (IHC staining of 0 or 1+; ISH single-probe average HER2 copy number < 4.0 signals/cell; or ISH dual-probe HER2/CEP17^a ratio < 2.0 with an average HER2 copy number < 4.0 signals/cell). (Wolff, Hammond et al. 2014):

^aAlso referred to as CEN17.

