5. Subsequent to the End of Treatment Visit, all patients will be followed at 12 (± 2) week intervals until study closure. These visits may be performed by telephone. However, for patients who discontinue study treatment in the absence of progression, survival assessments may be combined with Disease Assessment Visits, and conducted every 6 (± 1) or 9 (± 2) weeks until progression, and then at 12 (± 2) week intervals until study closure.
6. The End of Treatment Visit should be performed within 28 days after last dose of study treatment and prior to initiation of alternate therapies.
7. Assessments do not need to be repeated if completed within the previous 24 hours as part of the screening assessment.
8. Assessment of GPNMB expression (by IHC) will be performed at a central laboratory. Additional analyses to be performed centrally may also include GPNMB expression by RT-PCR, examination of tumor markers using IHC or other molecular analyses, evaluation of tumor infiltrating leukocyte populations, biomarkers related to immune activation, and localization of CDX-011, CR011, or MMAE at the tumor site. Sample collection, processing and shipping instructions will be provided separately.
9. Tumor specimen(s) submitted for screening must have been obtained in the setting of advanced disease. Submission of additional samples from other collection dates, when available, is encouraged. Tissue may be submitted and tested at any time prior to or during the 28-day window for screening, provided that the patient has signed an appropriate consent (either a tumor tissue-specific consent or full study consent).
10. In the event of a repeat resection or biopsy during treatment or following progression, submission of tissue sample for central analysis is strongly encouraged.
11. Determination of triple-negative status will be done at a local laboratory. Tumor sample(s) used to determine eligibility must be obtained in the setting of advanced disease. Laboratory reports will be required to provide quantitative results of sufficient detail to verify eligibility for all patients enrolled (see study entry criteria).
12. Medical history includes demography, race, ethnicity, history of breast cancer, previous therapy, and pre-existing diseases. At Cycle 1, Day 1, medical history is updated with any adverse events occurring prior to administration of study drug.
13. Complete physical exam should be performed at screening; thereafter, symptom-directed exams are acceptable.

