7.3 Study Day

Study Day represents the elapsed number of days from Study Day 1, inclusive.

Study Day $n = (\text{Date of assessment} - \text{Date of Study Day 1}) + 1$ day,

if Date of assessment \geq Date of Study Day 1. Or,

Study Day $n = (\text{Date of assessment} - \text{Date of Study Day 1}),$

if Date of assessment $<$ Date of Study Day 1. Unless otherwise specified, the timing of all study-related events, assessments, and interventions will be calculated relative to Study Day 1. Study Day -1 will be the day before Study Day 1, and in general, negative days will be measured backwards starting from Study Day -1 .

7.4 Cycle 1 Day 1

The first 21-day treatment cycle will begin with the first dose of study treatment, and will be denoted as “Cycle 1 Day 1”. In general, the start date of each cycle (i.e., Day 1 of Cycle k , where $k=1$ to maximum number of cycles started) equals the date of the first dose of study treatment administered in the corresponding cycle. If study treatment is permanently discontinued, then the cycle number and cycle day for study-related assessments done after the last cycle of dosing will be replaced in the tables, figures, and listings with the visit name (e.g., End of Treatment Visit, Disease Assessment Visit WK24). The visit date and study day also will be used to identify the timing of such assessments.

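### The quality-of-life time-point rule in SAP 10.7 can drop End of Treatment questionnaires from the by-week summaries, and the SAP does not say whether it also governs the longitudinal models

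*SAP*

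**What the plan says.** SAP 10.7 sets the schedule: "Post-baseline HRQOL assessments are planned for Day 1 of Cycles 3, 5, 7, etc", plus the EOT visit. The schedule of assessments (SAP Table 1, Protocol Table 1) has no questionnaire at Disease Assessment or Survival visits. EOT timing comes from footnote 6: "The End of Treatment Visit should be performed within 28 days after last dose of study treatment and prior to initiation of alternate therapies".

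For summaries, actual visits are used, "including unscheduled visits and EOT visits) mapped at Weeks 6, 12, 18, etc". If several share a time point, "the assessment performed closest to the planned study day will be used for purposes of summarizing the data". If two are equally distant, "the measurement occurring prior to the planned study day will be used for summarization". No window limits are given for the mapping.

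The models come later in the same section. The mixed model has a linear effect of week, a week-by-treatment interaction and an AR(1) covariance, with compound symmetry as fallback. The pattern-mixture model splits patients by whether their last HRQOL assessment came before 6 months. Neither description says whether the one-score-per-time-point rule applies. SAP 10.1 and 10.7 both class HRQOL as exploratory, with nominal p-values.

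**The concern.** The planned weeks coincide with odd-cycle Day 1, so the selection rule is not neutral between the two kinds of form. An on-schedule Day 1 score is at distance zero from the planned day and beats any later EOT score in the same slot. The form that loses is the one completed after the decision to stop, when progression or toxicity is most likely to show.

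SAP 10.7 itself warns that sicker patients leave the study, that the remaining scores then look misleadingly good, and that missing data are expected to follow worsening prognosis. A rule that sets aside scores actually collected at that moment works against this warning. At stake are the by-week descriptive tables and, depending on how the silence is read, the inputs to the two models.

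**Working it through.** **Plan's own figure.** There is none: the documents give no expected share of EOT forms kept or dropped.

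**Inputs from the documents**
- Cycle length 21 days (SAP 7.4): "The first 21-day treatment cycle will begin with the first dose of study treatment". Day 1 of Cycles 3, 5, 7, 9 is therefore Week 6, 12, 18, 24.
- EOT within 28 days of last dose (SAP Table 1, footnote 6).
- Last dose in a cycle (Protocol synopsis): "CDX-011 will be administered on Day 1 of repeated 21 day cycles"; "Capecitabine will be orally administered on Days 1-14 of repeated 21 day cycles".
- Scans at Weeks 6, 12, 18, 24 (plus or minus 1 week), then every 9 weeks (SAP Table 1, footnote 4).
- Median PFS 6.25 months (CDX-011) and 4.0 months (capecitabine) (SAP 5).

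**Assumptions.** Each form goes to the nearest of Weeks 6, 12, 18 and so on (bins of plus or minus 21 days); every patient completes an EOT form. The timing of EOT within its window and the rate of stopping without progression are also assumed.

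**Step 1: which stops lose the form (on-time dosing)**
- Last cycle odd, 3 or later: EOT less than 21 days after that Day 1 is in the same bin and is dropped. At 21 days or later it moves to the next bin and is kept.
- Last cycle even: EOT is at least 21 days after the previous odd Day 1, so it is kept.
- Last cycle is Cycle 1: there is no competing post-baseline score, so it is kept.

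**Step 2: odd-cycle stops, EOT uniform over its 28-day window**
- CDX-011, last dose Day 1: 21/28 = 75% dropped (20/28 = 71% if the visit cannot fall on the dosing day).
- Capecitabine, last dose Day 14 (13 days after Day 1): (21 - 13)/28 = 29% (7/28 = 25% if the visit cannot fall on the last dosing day). The share is higher if dosing stops earlier in the cycle.

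**Step 3: share of all EOT forms, by simulation.** Exponential PFS with the medians above, the protocol scan schedule, and Day 1 visits varying by plus or minus 3 days. The first two rows span no stopping without progression and such stopping at a median of 12 or 6 months; the last two use 12 months. Entries are CDX-011 / capecitabine.

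| Scan timing | EOT within 7 days of stopping | EOT evenly spread to day 28 after last dose | EOT at days 21-28 after last dose |
|---|---|---|---|
| -7 to +7 days, no reading delay | 37-42% / 39-44% | 26-30% / 22-27% | 6-7% / under 1% |
| -7 to +7 days, 5-day reading delay | 49-59% / 53-66% | 34-41% / 28-34% | 6-8% / under 1% |
| All 3-7 days early | 23% / 18% | 15% / 7% | 3% / under 1% |
| All 3-7 days late | 62% / 68% | 42% / 37% | 7% / under 1% |

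The overall range is about 0% to 68%. With evenly spread EOT and scans across the full window it is 22-41%.

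**Step 4: difference between arms.** With evenly spread EOT, CDX-011 loses about 4 to 8 percentage points more (smallest gap 30.3 - 26.5 = 3.8; largest 14.6 - 6.9 = 7.7). With prompt EOT the order usually reverses (59% against 66%, for example). The direction is not fixed.

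**Step 5: the 6-month split, an illustration.** Six months is 6 x 30.4375 = 182.6 days. Cycle 9 Day 1 is at 8 x 21 = 168 days. An EOT form 15 to 20 days later falls at 183 to 188 days, past 6 months, but is in the Week 24 bin and is dropped. If dropped forms do not count as the last assessment, this patient is classed as a dropout instead of a completer.

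**The case against.** The selection rule is worded twice as applying to summarization, and the models are specified separately. A reader might infer that the mixed model also loses these scores and that its missing-at-random assumption is weakened. There is some reason to: an AR(1) structure indexed on mapped week cannot hold two scores from one patient in one week, and no other selection rule is given. But the SAP does not say that the model uses mapped weeks, nor that it takes one score per week. The loss from the models is an inference from silence, and the documents do not establish it.

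A reader might also infer that an EOT form in the same slot is always farther from the planned day. That fails when dosing is off schedule. Odd-cycle visits have a window of plus or minus 5 days. If Day 1 is 5 days early, an EOT form 1 to 9 days later is nearer the planned day and is kept.

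Nor do the documents support a single headline loss. The bins are assumed, a last dose on Day 1 does not describe capecitabine, and late EOT visits lose almost nothing. The SAP does include EOT visits in the mapping, recognizes informative dropout and plans a pattern-mixture sensitivity analysis. No document shows how far dropped scores differ from retained ones, so any shift in the treatment contrast is unquantified.

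All of this stands, and it limits the point. It does not remove it: under a stated rule, and with no offsetting provision, on-schedule odd-cycle stops lose an observed EOT score from the summaries.

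**Conclusion.** The point holds for the by-week summaries. When dosing is on schedule and the last cycle is odd (Cycle 3 or later), an EOT score mapped to the same slot as that Day 1 score is dropped, although no other questionnaire is planned after the decision to stop. Even-cycle and Cycle 1 stops generally keep it.

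The size is conditional. Assuming bins of plus or minus 3 weeks, the share lost lies between about 0% and 68%, and is roughly 22-41% with evenly spread EOT and scans across their full window. It may differ by arm. These figures rest on bins, EOT timing and stopping rates that the documents do not give. Dose delays beyond 3 days were not modelled.

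For the mixed and pattern-mixture models the finding is only that the input data are unspecified. HRQOL is exploratory, so no confirmatory conclusion changes and severity is low.

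**What to change.** Amend SAP 10.7 in three places, before HRQOL data are summarized by arm:

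1. In the by-week tables, present EOT as its own row instead of letting it compete for a weekly slot, and state the mapping windows for the remaining visits.
2. State that the mixed and pattern-mixture models use every questionnaire at its actual assessment time, with a covariance that allows unequal spacing. Spatial power, the continuous-time analogue of AR(1), is one choice. Merely keeping all forms under AR(1) by assessment order would treat an EOT form a few days after Day 1 as a full six-week step.
3. State that EOT forms count as the last HRQOL assessment in the 6-month dropout/completer split.

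The cost is a few sentences of SAP text and minor programming. No new data are needed.
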